## 7.6/ Montreal Cognitive Assessment (MoCA)

The Montreal Cognitive Assessment tool ([www.mocatest.org](http://www.mocatest.org)) 8.1 will be administered by a study investigator at ICU and hospital discharge. Due to infection control concerns regarding the cleaning of tablet computers the test will be administered on paper. All study investigators will register and receive online training and certification in MoCA at the website listed above.

## 8/ Study Interventions

### Temperature management:

1. Therapeutic Hypothermia Arm: The participating ICUs share an established institutional protocol for NMB and TH, which will facilitate rapid mobilization of treatment following randomization. Sedation will be adjusted to achieve a RASS -4 score and cisatracurium (Nimbex™) will be initiated and adjusted to the lowest rate that achieves nerve stimulation response of 2 twitches in train-of-four monitoring, reduction in ventilator dyssynchrony to acceptable levels, and elimination of shivering. NMB will be continued through the rewarming phase at least until core temperature reaches 35.5°C (~54h total time). Note that if the supply of Nimbex in the Clinical Pharmacy is insufficient to treat the subject, a supply of study-only Nimbex is available in the Investigational Drug Service Pharmacy.

Since the objective of CHILL-pilot is to test the effectiveness of cooling to a target temperature rather than the performance of a specific cooling device, patients in the TH arm will be cooled using one of the institution's two FDA-approved surface cooling devices, Blanketrol II cooling blankets or Arctic Sun™ cooling system. Core temperature will be reduced to 34°-35°C as quickly as possible and TH maintained for 48h. Patients will then be rewarmed to 36°C by 0.3°C/h and the cooling device removed. Post-cooling fever suppression is not part of the CHILL-pilot protocol. Cooling parameters were selected to optimize risk:benefit ratio. The criteria for early termination of hypothermia are persistent severe bradycardia (heart rate < 30 associated with mean arterial pressure <65 without vasopressor agents), uncontrolled bleeding, and intractable ventricular arrhythmias.

### Placing the order to initiate hypothermia:

- Order sedation to RASS >-4 and Nimbex to achieve 2 twitches on train-of-four testing.
- Enter UMMC MED-CC Hypothermia Following Arrest Supplemental order set in Epic with the following modifications:
  - i. De-select: Capnography, CVP monitoring, SvO2 monitoring, NPO, Bair Hugger, Maintain MAPBP > 80 mmHg, Document Water temperature, CXR, sodium chloride 0.9% bolus, fentanyl, and vecuronium, cisatracurium.
  - ii. Under Chemistry, select Comprehensive Metabolic Panel
  - iii. Modify Hyper/Hypothermia order by changing stop date from 24h to 48 h and changing comments to: "Lower patient's temperature to **34 – 35C** as quickly as possible per protocol. Maintain **core temperature between 34 and 35C for 48 hours**. AT **48 hrs** after the initial cooling, re-warm patient no faster than **0.3** degree C per hour to **36C**." Delete "Then maintain ≤ 37C for 48 hours." (Changes from Epic order set are underlined and bolded.) These instructions have been added to the Randomization CRF.

2. Usual Temperature Management Arm: Controls will receive sedation and NMB as clinically indicated to achieve synchrony with the ventilator. During the 54h post-randomization period (corresponding with cooling and rewarming in the TH arm), acetaminophen will be given for core temperature  $>38^{\circ}\text{C}$  and surface cooling initiated for core temperature  $>38.5^{\circ}\text{C}$  and adjusted to maintain temperature  $\leq 38^{\circ}\text{C}$ . If patients are hypothermic (core temperature  $<35.5^{\circ}\text{C}$ ), surface warming will be initiated to restore core temperature to  $37^{\circ}\text{C}$ . Following the 54h treatment period, temperature management in both arms will be directed by the ICU team.

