
We have been approved for funding by Department of Defense (DoD) to support for a 4-year multicenter RCT of TH+NMB for 48h vs. standard of care with contract to be completed June 1, 2020 and with enrollment to begin in Fall of 2020. This study was designed prior to the onset of COVID-19, which is now the most common cause of ARDS and will likely continue to be in the Fall, 2020 and perhaps beyond. Therefore, it is important to decide whether patients with COVID-19 ARDS should be enrolled in our CHILL trial. Therefore, we will conduct a 20-patient pilot safety and feasibility trial of our CHILL TH+NMB treatment vs. control in COVID-19 patients with ARDS who meet the inclusion/exclusion criteria of our DoD-funded trial. The major objective of the proposed pilot trial is to determine whether it is safe and feasible to include patients with COVID-19 ARDS in our Phase IIb CHILL RCT of TH+NMB vs. control in patients with moderate to severe ARDS.

The pilot will be conducted at the University of Maryland Medical Center. To facilitate randomization within the inclusion window, we will consent and enroll based on partial fulfillment of randomization criteria and randomize once all criteria are met. Patients will be

eligible for enrollment when they have been diagnosed with COVID-19 by PCR, and have met all Berlin criteria for moderate to severe ARDS within the 48h inclusion window except the P/F ratio  $\leq 200$  but will not be randomized until P/F ratio (measured or imputed based on SpO2) is  $\leq 200$  (while on  $\geq 8$  cm H2O PEEP and  $\geq 0.6$  FiO2). We plan to randomize a total 20 patients over 4 months to hypothermia (core temperature 34°-35°C for 48h) plus NMB or usual temperature management. The primary outcome measures will be effectiveness of cooling in achieving and maintaining the target temperature and safety measures. Secondary outcomes will include 28-day ventilator-free days (VFDs), 28-day ICU-free days, oxygen saturation index (OSI), driving pressure, Sequential Organ Failure Assessment (SOFA) score, 60-day and 90-day survival, 90-day functional assessment, cognitive assessment at ICU and hospital discharge, and biomarkers of inflammation and lung injury. Since the nature of the intervention precludes blinding, all treatment and clinical decision making related to study outcomes will be protocolized and compliance with study protocols will be monitored.

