### 2.3.2 Coinvestigators

Coinvestigators from within the Division of Pulmonary and Critical Care Medicine (PCCM) and outside the division will have the following responsibilities:

1. Maintaining education and study procedure competency in their respective units
2. Assisting in the screening and enrollment of study participants from the participating units.
3. Assisting in obtaining informed consent.
4. Interpretation of clinical data (medical history, physiologic, laboratory, and radiographic) related to all study procedures (screening, enrollment, data recording, AE/SAE reporting).
5. Order-writing and implementation of study procedures
6. Being available to unit staff for study-related questions
7. Identification of protocol deviations and other reportable events and their correction
8. Identification of AEs/SAEs and assisting in their reporting
9. Assisting in obtaining and handling of biological specimens

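### The hypothermia order instruction asks for sedation to RASS >-4, but the intervention text for the same paralysed patients sets RASS -4

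*Protocol*

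**What the plan says.** Protocol Section 8, under Temperature management, describes the hypothermia arm: "Sedation will be adjusted to achieve a RASS -4 score", with cisatracurium started and run at the lowest rate that gives 2 twitches on train-of-four, acceptable ventilator synchrony and no shivering. On duration it says "NMB will be continued through the rewarming phase at least until core temperature reaches 35.5°C (~54h total time".

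The next block of Section 8, on placing the order to initiate hypothermia, opens with this bullet: "Order sedation to RASS >-4 and Nimbex to achieve 2 twitches on train-of-four testing".

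For the control arm the text is "Controls will receive sedation and NMB as clinically indicated to achieve synchrony with the ventilator", with no RASS score. RASS appears nowhere else in the Protocol or SAP, and the abbreviations list in Section 1.4 does not include it. Section 8 also notes that "The participating ICUs share an established institutional protocol for NMB and TH", but that institutional protocol is not reproduced.

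**The concern.** Both lines apply to the same patients at the same step: hypothermia arm, Nimbex, 2 twitches. They name different sedation targets.

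The doubtful line is the operational one. Section 2.3.2 lists "Order-writing and implementation of study procedures" among the coinvestigators' duties, and the order bullet tells them what to enter. The same block has staff de-select fentanyl, vecuronium and cisatracurium from the post-arrest order set, so the bullet is the manual's own order-level instruction for sedation and paralysis.

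Two things are at stake:

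- **Sedation depth.** On the usual scale the literal order permits lighter sedation than the intervention text, in patients who are paralysed.
- **Adherence.** The Synopsis (Section 1.1) promises protocolised treatment with compliance monitored, and Section 12 makes staff failure to follow the protocol reportable to the IRB within 5 business days. A patient held at -3 meets the order line and breaches the intervention text; a patient held at -4 does the reverse. The case report forms shown have no RASS field, so the trial data would not reveal which line was followed.

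**Working it through.** No formula applies to the discrepancy itself. The check is a comparison of the two lines.

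**Same patients?** Yes. Both lines sit in Section 8, both concern the hypothermia arm, and both pair the sedation score with cisatracurium to 2 twitches.

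**Can the two be reconciled?** The intervention text gives a single score, -4. The order line can be read in four ways:

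| Reading of the order line | Is -4 allowed? | Same as the single target of -4? |
|---|---|---|
| Literal: above -4 (-3, -2 and so on) | No | No |
| > meant as strictly deeper than -4 | No | No |
| > meant as ≥ -4 | Yes | No, it also allows -3 and above |
| > meant as -4 or deeper | Yes | No, it also allows deeper scores |

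Under either strict reading no score satisfies both lines. Under either inclusive reading -4 satisfies both, but the order line still allows scores that the intervention text does not.

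**Is it a lost symbol?** Probably not. A ≤ sign survives in the same order block, in the wording staff are told to delete: "Then maintain ≤ 37C for 48 hours". This makes a lost symbol less likely but does not rule it out.

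**Does anything else settle it?** No. The control arm has no RASS target. The randomisation form tells staff to start sedation, blockade and cooling, with no score.

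**Nominal size.**

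- Planned sample: 20, from Section 1.1 ("We plan to randomize a total 20 patients over 4 months to hypothermia").
- Allocation: 1:1 within proning strata (Section 3.3).
- Hypothermia patients: 20 / 2 = 10, nominally. Allocation within strata does not guarantee exactly 10.
- Blockade: about 54 h per patient as stated in Section 8. This is not a maximum, because blockade runs at least until core temperature reaches 35.5°C.

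**The case against.** The strongest reply is that this is an editorial slip. The intended value stands just above it, no RASS score is collected or analysed, and the primary outcomes are cooling performance and safety. Trained staff write the orders, and the ICUs share an institutional protocol for blockade and hypothermia. Much of this stands: a slip is the likeliest explanation and the analysis is untouched. But the institutional protocol is not in the documents, so it cannot be shown to correct the order line.

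Three narrower points also deserve weight.

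- **The direction of harm is assumed.** The documents do not define RASS, so lighter sedation follows only if more negative means deeper. Without that assumption the textual mismatch remains.
- **The sign may have been ≥.** The order block says its edits to the order set are underlined and bolded, and underlining is not visible in the text I worked from. An underlined > could therefore have been meant as ≥. The RASS bullet is not bolded and is not part of the edited order comment, so I cannot show that this happened. If it did, -4 would satisfy both lines, but the order would still allow lighter sedation than the intervention text.
- **The exposure figure is soft.** Ten patients at about 54 h each describes time under blockade, not time under a wrong sedation order. The documents do not say that RASS is tracked as a running target throughout blockade. The figure marks who could be affected and should not be read as an estimate of harm.

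**Conclusion.** The concern holds. The manual's only two RASS targets, for the same arm and the same step, differ on every reading examined, and nothing else in the documents reconciles them. The intervention text most likely gives the intended value. This is an inconsistency in a treatment instruction rather than a flaw in the design or analysis. It should be corrected because the line that staff act on is the one that departs from the stated target, and because on the usual RASS scale it departs towards lighter sedation under paralysis. Real exposure cannot be quantified from the documents.

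**What to change.** Change the first bullet of the order instruction in Section 8 to ask for sedation to RASS -4, leaving the 2-twitch Nimbex target as it is. If the clinical leads intend -4 or deeper, write that in both the intervention text and the order bullet.

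The cost is one line, or two if the target is restated in both places. Data collection and analysis do not change.

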### 6/ Study Visit Schedule/Schedule of Events (see Gantt chart below)

DAYS	-2	0	1	2	3	4	7	8-27	28	ICU DC	Hospital DC	60	90
Screening data, consent, enrollment, monitor for randomization	X												
Pregnancy test (F)		F											
Randomization, baseline data, start assigned temperature management		X											
Q2h vital signs (e.g. SpO2, mean airway pressure, core temperature)		X	X	X	X	X	X						
Temperature management protocol		X	X	X	X								
ABGs		A	A	A	A	A	A						
Basic metabolic panel, CBC (times per day)		2	2	2	2	2	1						
Blood sugars (times per day)		4	4	4	4	A	A						
Research blood sample collection		X	X	X	X	X	X						
Ventilator and respiratory parameters	X	X	R	R	R	R	R						
Fluid management		X	X	X	X	X	X						
NMB status	X	X	X	X	X	X	X						
Medication review (pressors, steroids, inhaled vasodilators)		X	X	X	X	X	X						

Monitor for AEs		X	X	X	X	X	X	X	X	x	x	X	X
Calculation 28-day VFDs, ICU-FDs									X				
MOCA										X	X		
Assess Vital and functional status		X	X	X	X	X	X	X	X	X	X	X	X

X = Required (time not specified)

A = When Available

R = Measured during daily reference measurements (0600-1000). When more than one value is available, the value obtained closest to 8 a.m. will be recorded.

F = Required on females of reproductive age.

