## 7/ Study Measurements

Both arms will receive the same standard of care procedures listed below.

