### 7.3/ 5.3 Blood Laboratory values data collection

Hematology (WBC, Hgb, Hct, Platelets), Chemistry (Potassium, Bicarbonate, BUN, Creatinine, Glucose, Magnesium, Phosphate, Albumin, Bilirubin AST/ALT results measured by standard of care and recorded as per study data collection requirements.

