- Indicate whether the patient received an inhaled vasodilator since randomization by checking the appropriate “Yes/No” box on line 23. If “Yes,” indicate which agent(s) by checking the appropriate box(es) and the total hours one or more of the agents were administered in the indicated field.
- Indicate if the patient received vasopressor support at any time since randomization by checking the appropriate “Yes/No” box on line 24. If “Yes,” check the box next to each of the agents that was received, the highest infusion rate (and units) received, and the total hours receiving any vasopressor support. If “no” skip to question 25.
- Beginning on line 25, record the highest and lowest values for each indicated laboratory value since randomization. If there is only one value, record it in the lowest value field, and click the single value box. If there are no data, check the “None” box.
- In the appropriate fields in table beginning on line 26, enter the lowest and highest blood glucose values (from finger sticks) and the date and time of the measurements for each 6-hour period since randomization. If there is only a single value, record in the “Lowest Glucose” field and check the “Single Value” box for that 6-hour time period. If there are no glucose measurements, click the “None” box for that 6-hour time period.
- Indicate all ventilator modes used since randomization by checking the appropriate boxes under line 27 and circle the mode used at 0800.
- Indicate whether the patient was extubated since randomization by checking the appropriate “Yes/No” box on line 28 and, if extubated, enter the time and date in the appropriate fields.
- Record the highest and lowest measured tidal volumes in ml during mechanical ventilation since randomization in the appropriate fields on line 29.
- Based on the EMR, estimate the total time since randomization in hours in which tidal volume exceeded 7 ml/kg during mechanical ventilation and record in field on line 30.
- Enter the highest and lowest PEEP and Mean airway pressure in cm H2O during mechanical ventilation since randomization in the appropriate fields on lines 31 and 32, respectively.
- If still intubated between 0600 and 1000 on the day after randomization, record the plateau pressure and associated PEEP measured in this time interval in the indicated fields beginning on line 33. If multiple values are present, enter the value closest to 0800. If no

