**USE VALUES FROM 24 HRS PRECEDING RANDOMIZATION**

If no values were obtained for clinical purposes during 24 hours preceding randomization, **the lab tests must be obtained after consent and before study procedures.**

If only single temperature measurement in last 24 hours, record in "Lowest" field and check "Single" box. If no temperature measurements check "None" box.

Temperature: Lowest   .  °C Highest:   .  °C Single  None

Site of temperature measurement:  Esophageal  Bladder  CVC  Peripheral

Systolic BP: Lowest    Highest    mm Hg Single

Mean arterial pressure: Lowest    Highest    mm Hg Single

Heart rate: Lowest    Highest    beats/min Single

Respiratory rate: Lowest    Highest    breaths/min Single

Was patient mechanically ventilated when the lowest respiratory rate occurred?  Yes  No

Urine output for 24 hrs preceding randomization:       ml

Total output for 24 hrs pre-randomization:       ml (includes negative CRRT balance)

Total intake for 24 hrs pre-randomization:       ml

Was Intake/Output data for 24 hours?  Yes  No If <24 hours, how many hours:   .

**Laboratory data (if only one value, record in "Lowest" field and click "Single" box; if no data, click "None" box):**

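### The comprehensive chemistry panel is ordered in writing only for the hypothermia arm, so post-baseline bilirubin, and with it SOFA, may be ascertained differently by arm

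*Protocol*

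**What the plan says.** **Hypothermia arm.** Protocol Section 8, under the steps for ordering hypothermia, adapts a post-arrest order set and adds: "Under Chemistry, select Comprehensive Metabolic Panel". It does not say how often or for how long that panel is drawn.

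**Control arm.** The usual-temperature paragraph of the same section covers sedation, neuromuscular blockade and temperature ("Controls will receive sedation and NMB as clinically indicated to achieve synchrony with the ventilator"). It contains no chemistry order.

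**Both arms.**
- The Section 6 schedule has one laboratory row, "Basic metabolic panel, CBC (times per day"), set at twice daily on Days 0 to 4 and once on Day 7. It is not split by arm.
- Section 7 opens with: "Both arms will receive the same standard of care procedures listed below". Section 7.3 then lists the liver tests: "Albumin, Bilirubin AST/ALT results measured by standard of care and recorded as per study data collection requirements". No frequency is given.
- The Baseline Data form requires missing laboratory values to be drawn ("the lab tests must be obtained after consent and before study procedures"), and bilirubin is on that form.
- From Day 1, staff "record the highest and lowest values for each indicated laboratory value since randomization" and tick a None box if there is nothing to record. The Day 1, 3, 4 and 7 forms shown all follow this pattern for bilirubin.

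**Outcome and analysis.** SOFA is a secondary outcome (Section 1.1), and Aim 3 (Section 1.2) expects lower scores with hypothermia. The SAP does not mention SOFA by name, does not say how it is scored, and has no rule for a missing component.

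**The concern.** Bilirubin is the hepatic item of SOFA. A comprehensive metabolic panel includes it and a basic one does not. (These are general facts; the documents do not state them.) After randomization, the only written instruction that would generate a bilirubin result applies to one arm. In the other arm, the result depends on what the ICU team orders in an open-label trial.

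If completeness differs, the SOFA comparison partly reflects who was tested:
- **Missing scored as normal:** control scores are understated and hypothermia looks worse.
- **Untested days dropped:** controls are represented by days on which someone had reason to order liver tests. Their scores are then probably overstated and hypothermia looks better.

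More testing in one arm could also reveal more liver-test abnormalities there. Section 1.1 makes safety measures a primary outcome, and Section 12 makes a difference between groups the trigger for reviewing tabulated adverse events. An uneven panel cannot be corrected after the data are collected.

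**Working it through.** The documents give no SD or effect for SOFA and no figure for bilirubin completeness, so there is no stated number to reproduce. The check is a reading of the text followed by an illustration of size.

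**1. What each source secures for bilirubin**

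| Period | Hypothermia arm | Control arm |
|---|---|---|
| Baseline | Required (Baseline Data form) | Required (same form) |
| Around the start of cooling | Comprehensive panel ordered (Section 8); frequency and duration not stated | No order; standard of care (Section 7.3) |
| Days 4 and 7, after the roughly 54 h treatment period | Not shown to continue; standard of care | Standard of care |

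The asymmetry is real but limited. It lies after baseline, and its length is unknown because the change from 24 h to 48 h in Section 8 concerns the Hyper/Hypothermia order, not the chemistry order.

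**2. Size if a missing bilirubin is scored 0**

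Understatement of mean control SOFA = (share of days with hepatic points) × (points on such days) × (excess share of control days without bilirubin).

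All inputs are assumptions: 15–30% of days carry 1–2 hepatic points, and 30–70% of control days lack bilirubin while hypothermia days are complete.
- Low: 0.15 × 1 × 0.30 = 0.045
- High: 0.30 × 2 × 0.70 = 0.42

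With wider assumptions (mean hepatic points per day 0.1 to 1.0, excess missingness 25% to 100%), the range is 0.1 × 0.25 = 0.025 to 1.0 × 1.00 = 1.0 point.

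**3. Set against what the trial can detect**

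A total of 20 patients (Section 1.1) at 1:1 (Section 3.3) gives about 10 per arm. The SAP states two-sided alpha 0.05 for ventilator-free days; the same is assumed here. For a single comparison of means with 80% power:

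Detectable difference = (1.960 + 0.842) × SD × √(2/10) = 1.253 × SD.

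For an assumed SD of 2, 3 and 4 this is 2.51, 3.76 and 5.01 points.

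**4. False-positive rate with no true difference, SD 3**

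Standard error = 3 × √0.2 = 1.342.
- Shift 0.42: 0.42/1.342 = 0.313. Rejection rate = Φ(0.313 − 1.960) + Φ(−0.313 − 1.960) = 0.0498 + 0.0115 = 0.061.
- Shift 1.0 (the extreme of the wider range): 0.116.

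**5. Size if untested days are dropped**

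The sign is likely to reverse. The size depends on how strongly clinicians' ordering follows severity. The documents give nothing on this, so it is not quantified.

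**The case against.** Three stronger readings are tempting, and the documents do not support them.

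- **That bilirubin is measured systematically with hypothermia and only by chance in controls.** Section 8 gives no frequency or duration, so a single draw fits its wording. Section 7.3 lists bilirubin as a standard-of-care result for both arms, the same daily forms with the same None box serve both arms, and baseline is required in both. Routine ICU testing may leave little difference.
- **That the bias runs in one direction, against hypothermia.** This holds only if missing is scored as normal. Dropping untested days points the other way.
- **That Section 8 flatly contradicts the same-procedures statement in Section 7.** The Section 7 list includes bilirubin, so choosing the wider panel can be read as bringing a borrowed order set into line with Section 7.3. The clearer mismatch is between the basic panel in Section 6 and the liver tests in Section 7.3, and that affects both arms.

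Two further points stand. SOFA is one of many secondary outcomes in a 20-patient feasibility pilot, and the plausible shift is well below what the trial can detect. Bilirubin is also not the only gap in SOFA: the daily forms shown have no field for a neurological score, and blood gases are recorded only when available. The safety-detection argument is thin as well, because liver tests are neither among the events prompted daily nor among the risks in Section 11.

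None of this removes the core. As written, the plan orders the wider panel after randomization in one arm only, requires no post-baseline bilirubin in the other, and has no rule for missing values.

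**Conclusion.** The concern holds in a limited form: post-baseline ascertainment of bilirubin may differ by arm, and the SOFA comparison could be biased as a result. Neither a difference in completeness nor a direction of bias is established by the documents. Under the assumed inputs, and only if missing is scored 0, control SOFA would be understated by about 0.04 to 0.42 points (up to 1.0 at the extreme of the wider assumptions). The detectable difference is 2.5 to 5.0 points. At 0.42 points and SD 3, the false-positive rate is about 6%.

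These figures rest on assumed SDs, hepatic points and missingness shares, on complete measurement in the hypothermia arm, and on the usual content of the two panels. The effect is small and does not touch the cooling outcome. It merits correction because the plan itself creates the difference and the remedy is cheap.

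**What to change.** **Protocol.** Reconcile Sections 6, 7.3 and 8 so that both arms have the same chemistry panel, including bilirubin, at the same times on Days 0 to 4 and 7. The blood is already scheduled to be drawn on those days.

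**SAP.**
- State how SOFA is scored, with one missing-component rule applied identically in both arms.
- Report bilirubin completeness by arm and day.
- Add a sensitivity analysis of SOFA without the hepatic item in either arm.

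**Cost.** A few lines of text and no extra blood draw. With one wider panel per scheduled day, the upper limit is 6 assays per control patient (Days 0, 1, 2, 3, 4 and 7), or about 60 for 10 controls. The number is lower where routine care already supplies the result. The SAP additions need no new data.
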